## 5. Sample size

The sample size was calculated according to Sikora et al. [31] who compared the efficacy of PBM to a placebo group (laser off). In that study, the mean and standard deviation (SD) of the VAS score in the placebo group at the end of treatment was  $2.417 \pm 2.918$ . Considering that acceptable improvement in the PBM group would be at least 10% after the intervention, we obtained an effect value ( $E$ ) = 2.17. The sample size was then calculated using a t-test for comparing the means of continuous variables, whose standardized effect size was 0.70 assuming a one-sided alpha error of 0.05 and a beta error of 0.20, resulting in 28 patients divided into two intervention groups.

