## 8. Statistical analysis

All data were analyzed using the Statistical Package for the Social Sciences 25.0 (SPSS). First, the collected data were submitted to descriptive analysis. Fisher's exact test was then used to determine whether statistically significant differences in systemic alterations, psychiatric disorders and medication use exist at T0 between the TENS and PBM groups.

The quantitative data (VAS score and unstimulated salivary flow) were analyzed using the Kolmogorov-Smirnov normality test to assess if the data are normally distributed, which

was confirmed based on the mean error. Two-factor ANOVA was used to analyze intergroup (TENS and PBM) and intragroup (repeated measures at T0, T1, T2 and T3) differences in mean VAS scores and unstimulated salivary flow. For this purpose, the assumptions of sphericity were tested using the Mauchly test. The post-test of intergroup and intragroup interactions was carried out based on Bonferroni corrections, as well as using the trend test of the interaction between time and intervention. A level of statistical significance of 95% was adopted for all tests.

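### The significance level is misworded and gives no sidedness, planning is one-sided while the main analysis is not, and 28 patients do not give 80% power under either reading

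*Combined protocol and SAP*

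**What the plan says.** Section 8 (Statistical analysis) has one sentence on the decision threshold: "A level of statistical significance of 95% was adopted for all tests". It does not say whether tests are one- or two-sided. The main analysis there is a two-factor ANOVA, group by time over T0 to T3, for VAS score and salivary flow, followed by Bonferroni-corrected post-tests and a trend test of the interaction.

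Section 5 (Sample size) plans on a t-test comparing two means, "whose standardized effect size was 0.70", and continues: "assuming a one-sided alpha error of 0.05 and a beta error of 0.20, resulting in 28 patients divided into two intervention groups". The inputs come from a published comparison of PBM with a switched-off laser. The placebo arm of that study had an end-of-treatment VAS mean of 2.417 with SD 2.918, and from a 10% improvement criterion the plan says "we obtained an effect value ( $E$ ) = 2.17".

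No section states which of TENS and PBM is expected to be better. The only directional statement, in Section 5, concerns improvement under PBM, which Section 3 makes the control treatment. The allocation ratio is not stated.

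**The concern.** Three things do not fit together.

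- A significance level is a type I error rate. The 95% in Section 8 is the complementary confidence level, and it stands in the only sentence that sets the threshold.
- Planning uses a one-sided alpha, while the F tests of the main analysis have no direction. With two groups at one time point, the F test is the two-sided t-test.
- The stated 80% power should follow from the stated effect, alpha and sample size, and it does not.

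The practical risk lies in how the result is read. This is a small, unblinded comparison of two treatments. A reader who believes it had 80% power could take a non-significant difference as evidence that TENS and PBM perform alike, when a true difference of 0.70 SD would be missed more often than found on a two-sided test. Leaving the side undeclared also leaves room to choose a one-sided test once the data are known.

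**Working it through.** **Inputs.** From Section 5: d = 0.70, alpha 0.05 one-sided, beta 0.20, 28 patients in total, SD 2.918. Assumption: 1:1 allocation, so n = 14 per arm. All figures in steps 1 to 5 are for a two-sample t-test at one time point.

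**1. Reproducing the plan's own figure.** By normal approximation, n per arm = 2(z₁₋α + z₀.₈₀)²/d².
- One-sided 5%: 2(1.645 + 0.842)²/0.49 = 25.2, so 26 per arm. The noncentral t gives 25.94, again 26 per arm or 52 in total.
- Two-sided 5%: 2(1.960 + 0.842)²/0.49 = 32.0, so 33 per arm. The noncentral t gives 33.02, so 34 per arm or 68 in total.

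The stated total of 28 is not reproduced. A one-sample or paired t-test with d = 0.70, one-sided, needs 14.07 patients. That number may have been used as the size of each arm, but the text does not show this.

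**2. Power at 14 per arm.** The noncentrality is d√(n/2) = 0.70 × √7 = 1.852, on 26 degrees of freedom.
- One-sided 5% (critical t 1.706): 56.3% (normal approximation 58.2%).
- Two-sided 5% (critical t 2.056): 43.0% (normal approximation 45.7%). The two-group F test gives the same 43.0%.

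**3. Splitting the shortfall.**
- 80 − 56.3 = 23.7 points, because 28 does not follow from the one-sided inputs.
- 56.3 − 43.0 = 13.3 points, from testing two-sided.
- Total: 37.0 points.

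At 26 per arm, where the one-sided 80% is met, going two-sided lowers power from 80.1% to 69.7%, about 10 points.

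**4. What 14 per arm can detect.** With 80% power at two-sided 5%, d = 1.10. At SD 2.918 this is 1.10 × 2.918 = 3.21 VAS points.

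**5. Other readings.**

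| Reading | One-sided 5% | Two-sided 5% |
|---|---|---|
| 14 per arm, d = 0.70 | 56.3% | 43.0% |
| 14 per arm, d = 2.17/2.918 = 0.744 | 60.7% | 47.4% |
| 28 per arm (not what the text says), d = 0.70 | 82.7% | 73.0% |

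No two-sided reading reaches 80%. A Bonferroni correction over an assumed four time points (alpha 0.05/4) would lower the 43.0% to 22.5%.

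**6. The repeated-measures ANOVA.** Its power needs a within-patient correlation ρ, which the plan does not give. As an illustration, assume compound symmetry, 14 per arm, no difference at T0 and 0.70 SD at T1 to T3. The mean difference is 0.525 SD.
- Group by time: noncentrality 28 × (0.525² + 3 × 0.175²)/4/(1 − ρ) on 3 and 78 df. Power is about 32%, 43% and 85% at ρ = 0.3, 0.5 and 0.8.
- Group main effect: d = 0.525/√((1 + 3ρ)/4). Power is about 49%, 39% and 31% at the same ρ.

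**The case against.** **The 95% is a slip.** A reader might infer that success would be declared whenever p < 0.95. Nothing in the plan supports that. The natural reading is 95% confidence, so alpha 0.05, and the level then agrees with Section 5. This stands: that part is a wording error.

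**No two-sided rule is written.** Section 8 never says two-sided, and the sidedness of the post-tests and trend test is simply missing. That also stands. The mismatch is an inference from the named F tests and not a clash between two stated values. The inference is sound for the F tests, and no stated direction would justify one-sided testing.

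**Sidedness is not the main cause.** A reader might conclude that the 80% fails because of the threshold conflict. The documents do not support this: on Section 5's own one-sided terms, power is already only 56%. Correcting the threshold would not restore 80%.

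**43% is not the power of the planned ANOVA.** Correct. Step 6 of the working shows that the group-by-time test could do better or worse depending on a correlation the plan omits. The 43% must be labelled as a single-time-point figure.

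**The planning effect is itself doubtful.** E = 2.17 is about 90% of 2.417, not 10% (0.24). E with d = 0.70 implies SD 3.10, not 2.918, which would turn 3.2 points into 1.10 × 3.10 = 3.4. The source compared PBM with placebo, not TENS with PBM. These weaknesses are real, but they do not rescue the 80%, which fails even when d = 0.70 is accepted.

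**Conclusion.** The point holds in this form: the threshold is misworded and lacks sidedness, planning and main analysis do not share a sidedness, and the stated power is not delivered under either. At d = 0.70 and 28 patients, power is about 56% one-sided and 43% two-sided, against a stated 80% that needs 52 or 68 patients in total. The larger part of the gap, about 24 of 37 points, is an arithmetic mismatch inside Section 5; about 13 points come from sidedness.

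These figures rest on 1:1 allocation, on the plan's own d, and on a t-test at one time point before any multiplicity correction. They do not measure the power of the repeated-measures ANOVA. If 28 had meant per arm, the one-sided 80% would be met (about 83%) but the two-sided would not (about 73%).

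**What to change.** **Section 8.** Replace the threshold sentence with: *All tests are two-sided at the 5% significance level, with 95% confidence intervals.*

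**Section 5.** Patients were seen from April 2021 to February 2022 and the text is in the past tense, so keep the one-sided planning assumption as the record of what was done. Add a corrected statement beside it:
- For a two-sided 5% t-test at one time point, 28 patients (14 per arm) give about 43% power at d = 0.70. They give 80% power only for d of about 1.10, or about 3.2 VAS points at SD 2.918, before any Bonferroni correction.
- Power for the group-by-time test is not given, because no within-patient correlation is stated.
- A non-significant result must not be read as similarity of TENS and PBM.

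**Cost.** A few sentences. No extra enrolment is needed; the downside is a less favourable stated power.
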